4.5.2 Discontinuation from Protocol Participation

A subject may be discontinued from protocol participation for the following reasons:

1. Subject voluntarily withdraws
2. Subject develops a medical condition that is a contraindication to continuing study participation
3. The IND Sponsor or regulatory authorities stop the protocol
4. The IND Sponsor and/or PI assess that it is not in the best interest of the subject to continue participation or that the subject's compliance with the study is not sufficient
5. Co-enrollment into a study in which other investigational research agents will be administered before the subject has completed the follow-up after the last WEVEE vaccine administration;

5 SAFETY AND ADVERSE EVENTS

5.1 Adverse Events

An adverse event (AE) is any untoward or unfavorable medical occurrence in a human subject, including any abnormal sign (e.g., abnormal physical exam or laboratory finding), symptom, or disease temporally associated with the use of study treatment, whether or not considered related to the study product.

Each AE will be graded according to the Table for Grading Severity of Adverse Events (see [Appendix IV](#)). The following guidelines will be used to determine when or not an AE should be recorded in the study database:

- From the time that subject signs the ICF, only AE that meet the definition of a SAE as described in Section 5.2 that occur within 24 hours of a screening visit will be reported.
- Solicited AEs (i.e, reactogenicity parameters) will be recorded in the study database per diary card entries for 7 days after each product administration and is not recorded with attribution assessments. Clinicians will follow and collect resolution information for any reactogenicity symptoms that are not resolved within 7 days.
- Unsolicited AEs and attribution assessments will be recorded in the study database from receipt of the first product administration through the visit scheduled for 4 weeks after each product administration. At other time periods between product administrations and when greater than 4 weeks after the last study product administration, only SAEs (as detailed in [Section 5.2](#)) and new chronic medical conditions that require ongoing medical management are recorded through the last study visit.

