4.2.6 Product Administration

Before Ordering Study Product: Pregnancy prevention counseling must be conducted, and pregnancy test results must be confirmed negative for females of childbearing potential. Subjects must be clinically evaluated with a medical history review and injection site assessment. Blood samples must be collected after randomization but prior to product administration per Appendix III.

Ordering Study Products: The site must follow standard operating procedures to order study product from the Pharmacy.

Product Administration Procedures: It is recommended, but not required, that the first vaccination be administered into the non-dominant arm. It is preferred, but not required, to alternate arms for a subsequent product administration, if applicable. When choosing an arm for the product administration, clinicians should consider whether there is an arm injury, local skin problem or significant tattoo that precludes the administration of the study product or will interfere with evaluating the arm after product administration. All product administrations will be administered IM into upper arm deltoid muscle by needle and syringe.

For groups receiving adjuvant, the adjuvant will be added by the site pharmacist prior to delivery to the clinic for administration.

Prior to each product administration, the syringe MUST be inverted 5 times. “*Inversion*” of a prepared syringe is defined as a gentle, complete 180 degree rotation, do not “*shake*” the syringe.

For the Second Product Administration: If a subject presents with fever or other signs of significant illness on the day of the product administration visit, do not order or administer study product. Unscheduled visits may be used to evaluate the subject’s condition and the administration visit should be rescheduled within the allowable visit window.

If a subject is undergoing evaluation and/or treatment for a medical condition at the time of the second scheduled administration visit, then vaccinations should be delayed until the condition has resolved or is considered stable. Contact the IND Sponsor for questions about resuming or discontinuing vaccinations as needed.

To schedule a product administration visit outside of the allowable visit window, the site must document PI approval.

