4.4 Pausing and Resuming the Study

4.4.1 Criteria for Pausing the Study

The Protocol Chairs, in consultation with site PI, will closely monitor and analyze study data as they become available and will make determinations regarding the presence and severity of AEs. The administration of study products and new enrollments will be paused and the IND Sponsor will be promptly notified according to the following criteria:

- **One** (or more) subject experiences a **SAE** assessed as related to the study product (with or without adjuvant).
- **Two** (or more) subjects experience the same **Grade 3 or higher AE** assessed as related to the study product (with or without adjuvant). Pause is not required for self-limited solicited reactogenicity (generally defined as resolved within 2 days of onset) following any study vaccination.
- **Three** (or more) subjects experience the same or similar **Grade 3 solicited AE** (other than injection site redness or swelling) lasting ≥ 24 hours.

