4.5.1 Discontinuation of Product Administrations

A subject may be discontinued from receiving study product for the following reasons:

1. Pregnancy;
2. Grade 3 adverse event assessed as related to the study product (with the exception that self-limited Grade 3 solicited reactogenicity does not require discontinuation of study injections);
3. Grade 4 adverse event assessed as related to the study product;
4. Immediate hypersensitivity reaction associated with the study product;
5. Intercurrent illness that is not expected to resolve prior to the next scheduled study product administration;
6. Treatment with systemic glucocorticoids (e.g., prednisone or other glucocorticoid) or other immunomodulators (other than nonsteroidal anti-inflammatory drugs [NSAIDs]), with the exception that study product administration may continue per site PI discretion if the next one occurs at least 2 weeks following completion of glucocorticoid treatment;
7. The IND Sponsor and/or PI assess that it is not in the best interest of the subject to continue receiving study product.

Subjects who receive at least one study product will continue follow-up according to the Schedule of Evaluations, except that the research sample collections will be discontinued for pregnant women or others in which it is contraindicated.

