Visit Windows: Schedule Visits 02A through 05 with respect to Day 0; Schedule Visits 05A through 9 with respect to Visit 05.

The following visit windows apply: Visits 02A and 05A (+1 day). Visits 03 and 06 (±3 day). Visits 04 and 07 (±7 days). Visit 05 (± 7 days). Visits 08 and 09 (±14 days).

**APPENDIX IV: ASSESSMENT OF RELATIONSHIP TO VACCINE
AND
GRADING SEVERITY OF ADVERSE EVENTS**

Assessment of Causality Relationship of an Adverse Event to Study Vaccine:

The relationship between an adverse event (AE) and the vaccine will be assessed by the investigator on the basis of his or her clinical judgment and the definitions below.

Definitely Related. The AE and administration of study agent are related in time, and a direct association can be demonstrated.

Probably Related. The AE and administration of study agent are reasonably related in time, and the AE is more likely explained by study agent than other causes.

Possibly Related. The AE and administration of study agent are reasonably related in time, but the AE can be explained equally well by causes other than study agent.

Not Related. There is not a reasonable possibility that the AE is related to the study agent.

For purposes of preparing data reports in which AE attributions are limited to “**Related**” or “**Not Related**”, in this protocol, the “**Definitely, Probably and Possibly**” attributions will be mapped to the “**Related**” category. The definitions that apply when these two categories alone are used are as follows:

Related – There is a reasonable possibility that the AE may be related to the study agent.

Not Related – There is not a reasonable possibility that the AE is related to the study agent.

Grading the Severity of Adverse Events:

The FDA Guidance for Industry (September 2007): “Toxicity Grading Scale for Healthy Adult and Adolescent Volunteers Enrolled in Preventive Vaccine Clinical Trials” is the basis for the severity grading of AEs in this protocol. Several modifications were made to the table as follows:

“Emergency room visit” is not automatically considered a life-threatening event; these words have been removed from any “grade 4” definition where they appear in the table copied from the guidance document.

Any laboratory value shown as a “graded” value in the table that is within the institutional normal range will not be severity graded or recorded as an AE.

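### Section 5.1 does not require non-serious, non-chronic Grade 3+ adverse events arising between Visit 04 and dose 2 to be entered in the database with attribution, although the related Grade 3+ pause and discontinuation rules have no time limit

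*Combined protocol and SAP*

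**What the plan says.** **Recording.** Section 5.1 has unsolicited AEs and their attribution entered from the first dose up to the 4-week visit after each dose (Visits 04 and 07 in Appendix III). It then continues: "At other time periods between product administrations and when greater than 4 weeks after the last study product administration, only SAEs" and new chronic conditions needing continuing care are entered, up to the last visit.

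**Assessment.** Grading and causality carry no such limit. Section 5.1 says "Each AE will be graded according to the Table for Grading Severity of Adverse Events", and its AE definition covers an "abnormal physical exam or laboratory finding". Appendix IV says "The relationship between an adverse event (AE) and the vaccine will be assessed by the investigator".

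**Action rules.** The second pause criterion in 4.4.1 counts two or more subjects sharing an event of at least Grade 3 that is "assessed as related to the study product (with or without adjuvant). Pause is not required for self-limited solicited reactogenicity". Section 4.5.1 allows further doses to be withheld for a "Grade 3 adverse event assessed as related to the study product" (self-limited solicited reactions excepted) or for a related Grade 4 AE. None of these has a time limit.

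**Safeguards.** Under 4.4.1 the Protocol Chairs, consulting the site PI, "will closely monitor and analyze study data as they become available and will make determinations regarding the presence and severity of AEs". The site PI ensures daily review of safety data, and the Protocol Safety Review Team (PSRT) sees summary reports weekly (8.8.1). Section 4.2.6 requires a history review before dosing. If a subject is being evaluated or treated for a condition when dose 2 is due, "then vaccinations should be delayed until the condition has resolved or is considered stable".

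**Analysis.** AEs and laboratory measures are both primary safety parameters (6.2.1). Section 6.4.3 tabulates AEs by severity and relationship, lists them per participant, and plots laboratory values from baseline and during the study.

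**The concern.** The rules that act on related Grade 3+ events apply throughout the trial, but the rule that puts such events in the database stops at Visit 04 and restarts with dose 2. The interval between comes just before re-exposure in a first-in-human trial.

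A first related, non-serious Grade 3 event in that interval does not trigger expedited reporting to the sponsor, which 5.3 reserves for SAEs. On its own it does not meet the two-subject pause criterion either. Database entry is therefore the routine path by which it would reach the AE tables and the PSRT members outside the site, such as the IND Medical Officer. Section 5.1 does not require that entry.

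Laboratory results at Visit 05 are the clearest case. Section 4.2.6 has blood drawn before the dose, so these results belong to the interval, and abnormal ones count as AEs by the protocol's own definition.

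**Working it through.** The plan gives no figure of its own on this point, so the check compares the recording windows in 5.1 with the visit days in Appendix III.

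**Inputs (Appendix III).** Visit 04 is Day 28 ± 7, so Days 21 to 35. Visit 05 (dose 2) is Day 56 ± 7, so Days 49 to 63. Visit 06 is 14 ± 3 days after Visit 05, and Visit 07 is 28 ± 7 days after Visit 05. No contact is scheduled between Visits 04 and 05.

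**Length of the interval (Visit 05 day minus Visit 04 day).**
- Nominal: 56 − 28 = 28 days
- Shortest: 49 − 35 = 14 days
- Longest: 63 − 21 = 42 days

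**Share of the time from dose 1 to Visit 07.**
- Nominal: 28/84 = 33%
- Lowest: 14/(49 + 35) = 14/84 = 17%
- Highest: 42/(63 + 21) = 42/84 = 50%

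These are shares of calendar time, not of risk.

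**CBC and ALT.** After dose 1 and through Visit 07 there are five scheduled draws (Visits 03, 04, 05, 06, 07). One of the five, Visit 05, falls in the interval. Both tests are repeated at Visit 06, 11 to 17 days later, against the unchanged Day 0 baseline. An abnormality that persists can be recorded then. One escapes AE entry only if it appears after Visit 04 and resolves by Visit 06, a span of 70 − 28 = 42 days nominally, or 14 + 11 = 25 to 42 + 17 = 59 days within windows.

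**Creatinine.** It is scheduled at Visits 01, 02 and 05 only. The one scheduled post-dose test is Visit 05, so 0 of 1 falls inside an AE recording window. The value itself is still collected and plotted.

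**Could 5.1 mean continuous recording?** The sentence on the 4-week visits, read alone, might suggest recording from the first dose to 4 weeks after the last. The next sentence rules that out, because it names other periods between doses and limits what is entered in them. Letters of Amendment #1 and #3 leave 5.1 unchanged. Letter #2 is not in the file and could not be checked.

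**Which events are affected.** SAEs and new chronic conditions are always entered, and solicited reactions are captured by the 7-day diary. Most clinical Grade 4 definitions in Appendix IV rest on hospitalization and so would be SAEs. What remains is mainly non-serious Grade 3 events and some Grade 4 laboratory values.

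**The case against.** The strongest reply is that 5.1 is a deliberate choice of 4-week windows and that nothing clinical is lost. Most of this stands. Every AE is still graded and causally assessed. Sections 8.2 and 9.6 describe a single enrolling site. Its PI is responsible for daily review of the safety data, decides on discontinuation with or through a designee (4.5), and sits on the PSRT, personally or through a designee, with the Protocol Chairs. Two related Grade 3 events would both come under that PI's review. Section 5.2 also lets some blood dyscrasias count as SAEs without hospitalization.

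A reader might infer that the pause rule would fail to fire. The documents do not support that. No section ties the count to database entries, and 4.4.1 refers to study data generally. The content of the weekly PSRT reports is not specified, so what they would omit is not known. A probability of a missed pause would need an assumed event rate and onset pattern, and the documents supply neither.

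A reader might also infer that Visit 05 laboratory data, and the only post-dose creatinine in particular, drop out of the analysis. They do not. The boxplots in 6.4.3 exclude no visit. They do not, however, carry an AE grade or attribution.

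The evidence on frequency also favours the plan. In the related CHIKV VLP Phase 1 trial, the seven laboratory AEs judged related were mild or moderate (8.5.1). In the Phase 2 trial, the 16 potentially related AEs were mild to moderate (1.4.1).

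Finally, the same recording limit applies from Visit 07 to Week 36 (252 − 84 = 168 days nominally), and the change proposed below leaves it alone. That is true. No further dose follows for the subject concerned, which is why the interval before dose 2 has priority. Going further would be the sponsor's choice.

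**Conclusion.** The point holds in a limited form. For 28 days nominally (14 to 42 within windows) before the second dose, the protocol does not require a non-serious, non-chronic, unsolicited Grade 3+ AE to be entered with grade and attribution. Followed as written, the plan can leave such an event out of the primary safety AE tables and listings and out of the database available to PSRT members outside the site.

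The gap is in the record, not in clinical assessment or in the laboratory values. Failure of the pause count is possible but not shown. Few events are expected, and no event rate is claimed. The conclusion rests on the text of 5.1 as it stands in the file and assumes that the Letter of Amendment not in the file did not change it. It is an optional, cheap improvement and should not be reported as an error in the plan.

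**What to change.** Add one sentence to 5.1: every unsolicited AE of Grade 3 or higher, including one based on a Visit 05 pre-dose laboratory result, is entered with its grade and attribution from the first administration through the visit 4 weeks after the last administration, or through Visit 05 for a subject not given dose 2.

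List the events from the Visit 04 to dose 2 interval separately from the 4-week-window AE tables, so that different observation periods are not mixed. Leave the rule for lower grades and the pause and discontinuation thresholds unchanged.

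The cost is a few extra AE entries and one listing. Visit 05 already includes an interim history, CBC, ALT and creatinine, and grading and causality assessment are already required. No new visit, blood draw or clinical judgment is needed.

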5.2 Serious Adverse Events

The term “serious adverse event” (SAE) as defined in US 21 Code of Federal Regulations (CFR) 312.32 as follows: “an adverse event or suspected adverse reaction is considered “serious” if, in the view of either the investigator or sponsor, it results in any of the following outcomes: Death, a life-threatening adverse event, inpatient hospitalization or prolongation of existing hospitalization, a persistent or significant incapacity or substantial disruption of the ability to conduct normal life functions, or a congenital anomaly/birth defect. Important medical events that may not result in death, be life-threatening, or require hospitalization may be considered serious when, based upon appropriate medical judgment, they may jeopardize the patient or subject and may require medical or surgical intervention to prevent one of the outcomes listed in this definition. Examples of such medical events include allergic bronchospasm requiring intensive treatment in an emergency room or at home, blood dyscrasias or convulsions that do not result in inpatient hospitalization, or the development of drug dependency or drug abuse.”

“Life threatening” refers to an AE that at occurrence, represented an immediate risk of death to the subject. An event that hypothetically may cause death if it occurs in a more severe form is not considered life-threatening. Similarly, a hospital admission for an elective procedure is not considered a SAE.

5.3 Adverse Event Reporting to the IND Sponsor

All AEs that meet the definition of a SAE must be reported from receipt of the first product administration through the last study visit by the study site and submitted on an expedited basis to the IND Sponsor, VRC, according to sponsor guidelines as follows:

- results in death
- is life threatening
- results in persistent or significant disability/incapacity

- requires unplanned inpatient hospitalization or prolongation of existing hospitalization
- is a congenital anomaly/birth defect in the offspring of a study subject
- is an important medical event that may jeopardize the subject or may require intervention to prevent one of the other outcomes listed above.

In addition, any event, regardless of severity, which in the judgment of an investigator represents a SAE, may be reported on an expedited basis.

The site investigator will communicate an initial SAE report within 1 business day of site awareness of occurrence to the IND Sponsor by data entry in the database. Any SAE entered into the study database will generate an automatic email notification to the IND Sponsor. The site must remove personal identifying information about the subject from SAE case reports before submission to the IND Sponsor.

A full written report by the site investigator should be submitted to the IND Sponsor within 3 working days and as soon as possible in case of death. In order for the IND Sponsor to comply with regulations mandating sponsor notification of specified SAEs to the FDA within 7 or 15 calendar days, the investigator must submit additional information as soon as it is available.

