Product: The investigational VRC-WEVVLP073-00-VP vaccine was developed by the Vaccine Research Center (VRC) and is composed of a mixture of WEE, EEE, and VEE VLPs in a 1:1:1 mass ratio filled into single-dose vials at a concentration of 78 mcg/mL. Adjuvant is an aluminum hydroxide suspension (alum) provided in a sterile, pyrogen-free suspension at a concentration of 5 mg/mL in 3 mL glass vials filled to 0.7 ± 0.10 mL. The alum dose is 500 mcg and will be mixed during preparation of each vaccine dose. VRC-PBSPLA043-00-VP is sterile phosphate buffered saline (PBS), 1.2 mL per vial prepared for human injection as a diluent.

Subjects: Up to 40 healthy adults ages 18 to 50.

Study Plan: Eligible subjects will be randomized to receive WEVEE alone or WEVEE plus alum in each dose group. The product will be administered as an intramuscular (IM) injection in the deltoid muscle via needle and syringe on Day 0 and Week 8. For all Groups, solicited reactogenicity will be evaluated using a 7-day diary card. Assessment of vaccine safety will include clinical observation and monitoring of hematological and chemical parameters at clinical visits throughout the study. Safety dose escalation reviews will occur to ensure the safety data support proceeding to the higher doses. The study requires about 9 clinic visits and 2 telephone follow-up contacts after each product administration. The study schema is shown below.

VRC 313 Vaccination Schema				
Group	Subjects	Dose	Day 0	Week 8
1	5	6 mcg	WEVEE	WEVEE
2	5		WEVEE + alum	WEVEE + alum
3	5	30 mcg	WEVEE	WEVEE
4	5		WEVEE + alum	WEVEE + alum
5	5	60 mcg	WEVEE	WEVEE
6	5		WEVEE + alum	WEVEE + alum
Total*	30	*Up to 10 subjects over target accrual are permitted to be allocated to any group if needed for additional safety or immunogenicity evaluations.		

Study

Duration: Subjects will be evaluated for 36 weeks following the first vaccine administration.

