8.5.4 Other Risks

Blood collection procedures are common in routine medical practice. The risks of blood sample collection are minimal and consist of mild discomfort at the blood collection site. The procedure may cause mild pain, bruising, fainting, and, rarely, infection at the blood collection site.

We do not know the possible effects of the study vaccine on the fetus or nursing infant. Therefore, females of childbearing potential will be tested for pregnancy prior to each product administration.

It is possible that the standard medical tests performed as part of this research protocol will result in new diagnoses. Depending on the medical findings and consequences of being provided with the new medical information about health status, the study subject may view this aspect of study participation as either a risk or a benefit. Any such information will be shared and discussed with the subject and, if requested by the subject, will be forwarded to the subject's primary health care provider for further workup and management.

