APPENDIX II: CONTACT INFORMATION

APPENDIX III: SCHEDULE OF EVALUATIONS

		Screen	VRC 313 Schedule of Evaluations									
Visit		*01	02	02A	03	04	05	05A	06	07	08	09
Week of Study		-4 to 0	W1	W1	W2	W4	W8	W9	W10	W12	W24	W36
Day of Study		-28 to 0	D0 ¹	D2	D14	D28	D56	D58	D70	D84	D168	D252
Clinical	Tube											
VRC 313 Informed Consent		X										
VRC 313 AoU		X										
² Physical exam for eligibility, height /weight /vital signs and targeted exam (as needed) at other visits.		X	X		X	X	X		X	X	X	X
Medical history targeted to eligibility at screening; then interim medical history		X	X		X	X	X		X	X	X	X
³ Study product administration			X				X					
Phone evaluation (clinic visit as needed)				X				X				
Begin 7-Day Diary Card			X				X					
⁴ Pregnancy test: urine (or serum)		X	X				X				X	
Counseling on pregnancy prevention/ Reproductive Information Form		X	X		X	X	X		X	X	X	X
CBC, differential, platelet count	EDTA	3	3		3	3	3		3	3	3	3
ALT	SST	4	4		4	4	4		4	4	4	4
Creatinine	SST	X	X				X					
HIV ELISA (Western blot or PCR, if needed)	SST	4										
Research												
Antibody assays and serum	SST	*16	32		16	32	32		16	32	16	16
Daily Volume (mL)		27	39	0	23	39	39	0	23	39	23	23
Max. Cumulative Volume (mL)		27	66	66	89	128	167	167	190	229	252	275

* Screening: Most screening evaluations must be no more than 28 days prior to Day 0 to be used for eligibility (pregnancy test on Day 0 must be used for eligibility). If clinical assessment on Day 0 suggests significant changes may have occurred since screening, then physical examination and laboratory studies done on Day 0 are used for eligibility.

¹ Day 0=day of randomization and first product administration. Day 0 evaluations prior to first product administration are the baseline for assessing adverse events subsequently.

² Screening visit includes a physical exam with vital signs. At other visits a physical examination is done if indicated by interim history or laboratory test results. Otherwise only blood pressure (BP), pulse, and temperature are required.

³ Study product administrations: Complete post vaccination evaluations (BP, pulse, temperature, respiration and product administration site assessment) at 30 minutes or longer after each product administration. Subjects who receive only one product administration are expected to continue with follow-up through study Week 36.

⁴ Negative pregnancy test results must be confirmed for women of reproductive potential prior to product administrations.

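### SAE reporting closes at Visit 09, before any term birth conceived after dose 2 and most conceived after dose 1, although a birth defect in a subject's offspring is a listed SAE

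*Combined protocol and SAP*

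**What the plan says.** Section 5.3 sets the period for reporting to the sponsor: "All AEs that meet the definition of a SAE must be reported from receipt of the first product administration through the last study visit". The list that follows includes an event that "is a congenital anomaly/birth defect in the offspring of a study subject". Section 5.1 uses the same end point for the database. More than 4 weeks after the last dose, only SAEs and new chronic "medical conditions that require ongoing medical management are recorded through the last study visit".

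The Précis fixes the length of follow-up: "Subjects will be evaluated for 36 weeks following the first vaccine administration". In Appendix III, Visit 09 is Week 36, Day 252, and the window is "Visits 08 and 09 (±14 days". The same appendix says "Subjects who receive only one product administration are expected to continue with follow-up through study Week 36".

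Section 4.5.1 names pregnancy as a reason to stop product administration and then says "Subjects who receive at least one study product will continue follow-up according to the Schedule of Evaluations"; its only exception for pregnant women is that research samples stop. Section 8.5.4 says "We do not know the possible effects of the study vaccine on the fetus or nursing infant". Pregnancy tests are scheduled at screening, Day 0, Visit 05 (Day 56) and Visit 08 (Day 168). Letters of Amendment 1 and 3 leave the SAE period unchanged.

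**The concern.** The protocol treats fetal risk as unknown and makes a birth defect a reportable SAE, but it stops SAE reporting on a date tied to vaccination and not to the end of a pregnancy. Many anomalies become known at birth, so what matters is whether a birth can fall before Visit 09. The Visit 08 test shows the problem well. No doses remain at that point, so the result guides no dosing decision. A pregnancy begun after dose 2 and found there cannot reach term by Visit 09.

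SAEs are among the primary safety endpoints in Section 6.2.1, and this is a first-in-human product. Without a rule, the site has no stated duty to learn a later outcome or to send it to the sponsor.

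**Working it through.** **Inputs from the documents**
- Dose 2 at Visit 05: Day 56 ±7 (Appendix III).
- Visit 09: Day 252 ±14 (Appendix III).
- Visits 05A to 09 are counted from Visit 05. If dose 2 is not given, all follow-up is counted from Day 0 (Section 4.2.5).

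**Assumption, not in the documents.** Time from conception to birth is gestational age minus 2 weeks:
- 37 weeks: 35 × 7 = 245 days
- 39 weeks: 37 × 7 = 259 days
- 40 weeks: 38 × 7 = 266 days

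**The plan's own figure.** 36 weeks × 7 = 252, which agrees with Day 252.

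**Conception after dose 2 (given on day V)**
- Visit 09 is V + (252 − 56) = V + 196, and at the latest V + 196 + 14 = V + 210. A shift in Visit 05 moves Visit 09 equally, so the 210 days do not change.
- Gap at 37 weeks: 245 − 210 = 35 days. At 39 weeks: 259 − 210 = 49 days. At 40 weeks: 266 − 210 = 56 days.
- Against the nominal Visit 09 (V + 196), the gaps are 49, 63 and 70 days.
- If the test before dose 2 missed a conception up to 14 days earlier, the smallest gaps are 245 − 14 − 210 = 21 days and 266 − 14 − 210 = 42 days.

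Each of these gaps is positive, and each is a minimum because a later conception widens it.

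**Conception on or after Day 0.** The latest conception day that still delivers by Visit 09 is the day of Visit 09 minus the time to birth:

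| Visit 09 falls on | 37 weeks | 39 weeks | 40 weeks |
|---|---|---|---|
| Day 252 (nominal) | Day 7 | none (−7) | none (−14) |
| Day 266 (one dose, latest: 252 + 14) | Day 21 | Day 7 | Day 0 |
| Day 273 (two doses, both windows late: 63 + 196 + 14) | Day 28 | Day 14 | Day 7 |

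The last row is generous. It needs a conception by Day 28 to go undetected by a pregnancy test on Day 63, five weeks later. Counted as days on study, the 37-week column covers 8 of 253 days (3.2%) at the nominal visit and 29 of 274 days (10.6%) in the last row.

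**What follow-up to birth would need.** For conception up to Day 56, a 40-week birth falls as late as Day 56 + 266 = 322 (Week 46). For conception up to Day 252, it falls as late as Day 252 + 266 = 518 (Week 74).

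**The case against.** The strongest objection is that part of the record is unseen. The consent form is Appendix I of the protocol and was removed before review; Section 8.3 says it covers all aspects of participation. Section 5.3 refers to sponsor guidelines that are not supplied. Appendix III lists a Reproductive Information Form at every clinic visit without describing its content. Letters of Amendment 1 and 3 are supplied, but Letter 2 is not. Any of these could provide for contact about pregnancy outcome. This stands, and it rules out high confidence. It does not alter the end point written in 5.1 and 5.3, which has no exception or cross-reference.

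Second, a reader might infer that birth defects cannot be captured at all, or that every term birth falls after the last permitted Visit 09. The documents do not support that. Preterm births and anomalies found before birth can fall inside the period. So can some term births conceived in the first weeks after dose 1, as the table shows. A conception up to 14 days before Day 0 and missed by that day's test would deliver between Day 231 (245 − 14) and Day 252 (266 − 14), within reach of the nominal visit. Section 5.3 also speaks of a study subject's offspring without limiting this to women, so a birth to a partner already pregnant at Day 0 could be captured.

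Third, a reader might infer that a late birth defect would be recorded as the absence of an SAE, or that it could not be reported. No text says either. Section 5.3 permits an investigator to report any event judged to be an SAE, and the unanticipated-problem route to the IRB in Section 5.4.1 gives no cutoff date. Both leave reporting open, but neither creates a duty to follow a pregnancy or sets a later end date.

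Fourth, pregnancies should be few. There are 30 to 40 subjects of both sexes, contraception is required through the last visit, planned pregnancy is an exclusion, and tests precede each dose. No escalation, pausing or analysis decision is shown to depend on this point. That limits its weight, though the cost of the fix shrinks with rarity too.

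**Conclusion.** The concern holds as a gap in a stated rule. For conceptions after dose 2, reporting closes at least 35 days before a 37-week birth and 56 days before a 40-week birth, or 21 and 42 days if a conception up to 14 days earlier was missed by the test. For conceptions after dose 1, a term birth is captured only when conception falls in the first days or weeks: at best Day 28 for 37 weeks, Day 14 for 39 weeks and Day 7 for 40 weeks.

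The result rests on an assumed 245 to 266 days from conception to birth and on the visit windows in Appendix III. Confidence is moderate because of the unseen documents. The label is cheap improvement: the practical impact is small, and the point concerns data collection only.

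**What to change.** In Section 5.3, with matching text in 5.1 and 4.5.1, state two things:
- any pregnancy identified from first product administration through the last study visit is followed to its outcome by telephone or record request;
- a congenital anomaly from that pregnancy is reported as an SAE even when it becomes known after Visit 09.

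If the consent form, sponsor guidelines or another document already provides for this, 5.3 should say so and refer to it.

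The cost is a short letter of amendment, one or two contacts per pregnancy, and possibly a late addendum to the database. A pregnant subject's file would stay open for weeks to months after Visit 09.
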